17.3.3 Safety evaluation methods and criteria

1) DLT (Dose Limiting Toxicity)

Dose Limiting Toxicity (DLT) is evaluated from the first day of investigational drug administration up to 4 weeks post-administration. DLT is defined as adverse reactions of Grade 3 or higher according to the WHO Toxicity Scale, or severe adverse reactions classified as Grade 3 by Spilker's three-tier classification method, excluding adverse reactions associated with coronary artery bypass grafting (CABG).

Adverse reactions specific to CABG caused by the surgery itself are excluded from the DLT evaluation.

1. Blood test findings (in cases recovered without complications)
 - (1) Hemoglobin: 8-17
 - (2) WBC: 4-25
 - (3) Platelet: 50-550
 - (4) Bilirubin: 0.3-10.6
 - (5) GOT/GPT: 9-125/8-350

- (6) Alk. Phosphatase: 35-180
- (7) BUN/Cr: it depends on the patient's preoperative kidney function
- 2. Reoperation due to bleeding: occurs in 5-10% of cases.
- 3. Fever: A persistent fever above 39°C is rare unless pulmonary complications or infections occur. Therefore, a fever above 39°C lasting more than 24 hours is considered outside the range of common complications.
- 4. Infection: Mediastinitis occurs in 2-3% of cases.
- 5. Arrhythmia: Atrial fibrillation occurs in 20-30% of cases. Transient premature ventricular contractions (PVCs) are common, but the occurrence of multifocal PVCs is considered abnormal. Ventricular tachycardia and fibrillation may occur due to postoperative bleeding, myocardial dysfunction, or reperfusion injury in chronically ischemic areas. If these are clearly related to surgery, such as bleeding from the graft or cardiac tamponade, they are considered surgical complications. However, unexplained ventricular arrhythmias can occasionally occur. Recurrent ventricular arrhythmias are uncommon in patients discharged after surgery. If the patient had recurrent ventricular arrhythmias before surgery with a consistent pattern and interval, these are not considered caused by gene therapy, but follow-up with Holter monitoring is needed to track any changes.

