- 6. Allergic reactions: Occasionally, skin rash or bronchospasm occur after contrast agent use for preoperative imaging tests (coronary angiography, CT, MRI). Skin rash, bronchospasm, or anaphylactic shock can also occur due to blood transfusion reactions before or after surgery. These reactions typically occur immediately after administration of the causative agent and can usually be distinguished from reactions caused by gene therapy. However, since gene therapy is administered during surgery, which often involves transfusions, distinguishing the cause can be difficult. It is important to identify parameters such as rash occurrence or increased airway resistance on the ventilator immediately after surgery or during surgery—especially before and after gene injection—to clarify causality.

Assessment of adverse reactions related to coronary artery bypass grafting (CABG)

- 1. If continuous bleeding occurs after surgery (500 cc in the first hour, 400 cc/hr for the first 2 hours, 300 cc/hr for the first 3 hours) requiring re-thoracotomy, and surgical findings reveal that the bleeding is not from the gene injection site but rather from side branches of the graft, anastomosis sites, or diffuse bleeding at the wound caused by antiplatelet agents used to prevent graft occlusion, this is considered a surgical complication rather than an adverse reaction to gene therapy.
- 2. In cases of postoperative mediastinitis, only if the sterile distilled water used to dissolve the gene tests positive in culture for the same pathogen isolated from the patient is the complication considered related to gene injection. Otherwise, it is determined to be an infection related to CABG.
- 3. If complications such as skin rash or bronchospasm occur after blood transfusion, antibiotic injections, or contrast-enhanced tests following surgery, these will be evaluated by an allergy specialist to determine any association with gene therapy. If no causal relationship with the administered gene is found, the reactions will be regarded as general adverse reactions related to CABG.

4. Other adverse reactions characteristic of CABG mentioned above will be classified as surgery-related complications.

Reactions due to surgery listed under WHO toxicity scale items

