According to the WHO Toxicity Scale, toxicities of Grade 3 or higher are generally considered dose-limiting. However, since this clinical trial includes surgery, the following reactions caused by surgery are excluded from the DLT (Dose-Limiting Toxicity) evaluation:

Adverse events caused by coronary artery bypass graft (CABG) surgery are excluded from the DLT evaluation.

1. Hematology

- Hemoglobin: Decrease due to surgical bleeding that recovers with transfusion.
- Hemorrhage: Common post-operative complication. However, persistent bleeding at the gene injection site should result in discontinuation of dose escalation.

2. Gastrointestinal

- Bilirubin: Elevation up to 10.6 due to intra-body retention of hematoma after surgery is considered a normal response.
- GOT/GPT (AST/ALT): Levels up to 125/350 are excluded if attributable to transfusion or myocardial ischemia.

3. Renal / Bladder

- Proteinuria: If caused by pre-existing diabetes or renal failure.
- Hematuria: If caused by trauma during Foley catheter insertion.

4. Pulmonology: Findings due to decreased cardiac function.

5. Fever: Fever above 39°C lasting less than 24 hours (unless associated with pulmonary complications or infection).

6. Allergic Reactions: When the cause is clearly identified, such as contrast agents, antibiotics, or blood transfusion.

7. Cardiac

- Rhythm: Arrhythmias are unavoidable due to surgical dissection of the myocardium. While ventricular arrhythmias may occur due to reperfusion of chronically ischemic areas, establishing a direct association with gene injection is difficult. However, in the interest of patient safety, WHO Grade 3 criteria will be followed and dose escalation will be discontinued.
- Cardiac Function: Most patients have impaired cardiac function due to the nature of cardiac surgery; thus, excluded from DLT evaluation.
- Pericarditis: Most cases involve post-operative accumulation of blood or fluid in the pericardial space. Surgery may be necessary, but dose escalation will be discontinued only if bleeding is confirmed at the gene injection site.

2) TD (tolerated dose) evaluation

Subjects are enrolled sequentially, starting from Step 1, to determine the tolerated dose as follows:

1. Step 1: Three subjects are enrolled. DLT (Dose-Limiting Toxicity) is evaluated 4 weeks after the third subject is dosed.
 - 1-1. If no DLTs occur in any of the 3 subjects (0/3) → Proceed to Step 2 and enroll 3 more subjects (A)

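### Section 17.3.3 does not settle whether a severe postoperative allergic reaction of undetermined cause counts as a DLT

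*Combined protocol and SAP*

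**What the plan says.** All the relevant text is in section 17.3.3, part 1) DLT, of the combined protocol and SAP.

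- **Definition.** A DLT is a WHO Grade 3 or higher reaction, or a Spilker-severe one, from first administration to 4 weeks. Reactions associated with CABG are taken out.
- **CABG attribution rules, item 3.** When complications such as rash or bronchospasm "occur after blood transfusion, antibiotic injections, or contrast-enhanced tests following surgery, these will be evaluated by an allergy specialist", the specialist looks for an association with the gene therapy. The rule then ends: "If no causal relationship with the administered gene is found, the reactions will be regarded as general adverse reactions related to CABG".
- **WHO-scale list of surgical reactions excluded from DLT, item 6.** "Allergic Reactions: When the cause is clearly identified, such as contrast agents, antibiotics, or blood transfusion".
- **Background list of reactions specific to CABG, item 6 (Allergic reactions).** On contrast and transfusion reactions: "These reactions typically occur immediately after administration of the causative agent and can usually be distinguished from reactions caused by gene therapy". It then adds a caution about the operation itself: "since gene therapy is administered during surgery, which often involves transfusions, distinguishing the cause can be difficult".

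The synopsis repeats only the general exclusion of reactions accompanying CABG. Section 18.1 defines five causality categories and requires two or more investigators to assess the causality of a DLT or an unexpected Grade 3 or higher event. It does not say which categories make an event a DLT.

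**The concern.** The two rules ask different questions. Item 3 asks whether a link to the gene has been found. WHO-list item 6 asks whether another cause has been clearly identified. They agree when the cause is known. They can part when the specialist can neither implicate the gene nor identify another agent.

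The setting is an ordinary part of this trial. Section 13.4.4 schedules coronary angiography the day after surgery, section 13.5.1 lists postoperative antibiotics, and section 14.2 has staff watch on postoperative days 3 to 6 for allergic reactions that may come from the gene therapy. All of this falls inside the 4-week DLT window. An inconclusive review is possible: the product is given once, so the criteria on stopping and rechallenge tell the assessor little, and section 17.3.3 discourages skin testing.

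DLT is a primary endpoint and its count drives escalation. In an open-label trial with three to six subjects per dose, this rule should not be settled after the event has been seen.

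**Working it through.** **1. Which events are affected.** In Appendix 5, allergic Grade 3 is bronchospasm needing parenteral therapy and Grade 4 is anaphylaxis. Anaphylaxis is not named in item 3, but that item's examples are not exhaustive. Erythema alone is cutaneous Grade 1; the Grade 3 entry describes desquamation and ulceration. So only severe events matter, and only those still unexplained after review.

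**2. The rules side by side.**

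| Finding of the review | Attribution item 3 | WHO-list item 6 |
|---|---|---|
| Another cause clearly identified | not a DLT | not a DLT |
| Gene implicated | not excluded | not excluded |
| Undetermined | literally: no link found, so not a DLT | cause not clearly identified, so a DLT |

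**3. Do neighbouring rules supply a default?** They point in opposite directions. Mediastinitis is tied to the injection only if the diluent culture grows the same pathogen: "Otherwise, it is determined to be an infection related to CABG". For ventricular arrhythmia of uncertain cause, "in the interest of patient safety, WHO Grade 3 criteria will be followed and dose escalation will be discontinued".

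**4. The plan's own figures.** Three dose groups of 3 give 3 × 3 = 9 subjects, and expansion of every group gives 3 × 6 = 18. Both match section 11.4 and are unaffected.

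**5. Effect of one undetermined severe event.** The rules in 17.3.3, part 2), are: 0/3 escalates; 1/3 adds three subjects and escalates only if all three are clean; 2/3 or 2/6 stops. Let b be the assumed rate of other DLTs per subject. The chance that three added subjects are clean is (1 − b)³: 1.000, 0.857, 0.729 and 0.512 for b = 0, 5, 10 and 20%. The added subjects are assumed to have no further undetermined allergic event.

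| Situation at the dose | Event excluded | Event counted |
|---|---|---|
| No other DLT in first three | 0/3, escalate | 1/3, add three; escalates with chance (1 − b)³ |
| One other DLT in first three | 1/3, add three; escalates with chance (1 − b)³ | 2/3, stop (chance 0) |
| One other DLT in six | 1/6, escalate | 2/6, stop (chance 0) |

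In the first row, counting the event also means six subjects instead of three and at least 4 more weeks of observation. In the third dose group there is no further escalation; what changes is the expansion or the tolerated dose (C or B).

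**6. Unconditional size, under assumed rates.** Let a be the rate per subject of an undetermined severe allergic event. The documents give none.

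- Chance of at least one in 9 subjects, 1 − (1 − a)⁹: 0.9%, 4.4% and 8.6% for a = 0.1, 0.5 and 1%.
- Chance of passing a dose level: E(p) = (1 − p)³ + 3p(1 − p)²(1 − p)³, with p = b if such events are excluded and p = 1 − (1 − a)(1 − b) if they are counted.
- For b = 10% and a = 1%: p = 1 − 0.99 × 0.90 = 0.109, and E falls from 0.906 to 0.891, or 1.5 points.
- Over a = 0.1 to 1% and b = 0 to 20%, the fall runs from 0.0 to 1.7 points.
- Higher assumed rates give more. With b = 10% and a = 2, 5 or 10%, E is 0.875, 0.824 or 0.730 against 0.906.

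**The case against.** The strongest reply is that the two rules fit together. Item 3 is an attribution procedure: it sets no grade threshold and does not mention DLT. WHO-list item 6 belongs to the list that says which Grade 3 or higher reactions leave the DLT count, and it names the same three triggers. On that view the specialist reviews first, and exclusion of a severe event then needs a clearly identified cause. Moreover, section 18.1 has a possibly-related category for an event equally likely to come from the product or another cause, and such an event sits badly with a statement that no causal relationship was found.

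Much of this stands. The harmonised reading is plausible and already gives the result sought here. It does not close the gap, because the general CABG exclusion in the DLT definition also reaches whatever item 3 labels CABG-related, no sentence gives the WHO list precedence, and the causality categories are not tied to DLT status.

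A reader might infer more than the documents support:

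- **That the plan definitely excludes unexplained reactions.** It does not say so; that is one reading of item 3.
- **That the plan admits these reactions are hard to attribute.** Its remark about difficulty concerns transfusion during surgery. Item 3 covers the period after surgery, and the same background item says transfusion and contrast reactions can usually be told apart from gene therapy reactions.
- **That the effect on escalation is large.** Falls of about 3 to 18 points appear only at assumed event rates of 2 to 10% (with b = 10%), for which the documents offer no basis.

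**Conclusion.** The point holds as a minor ambiguity in the definition of a primary safety endpoint. For a severe postoperative allergic reaction that remains undetermined after specialist review, two classifications are open and the plan does not choose. Conditional on such an event, the step taken under the escalation rules differs in every situation examined. Unconditionally the effect is small if the event is as uncommon as supposed: at most about 1.7 percentage points in the chance of passing a dose level, for assumed rates up to 1% and other DLTs up to 20%. These rates are illustrations, not figures from the documents. The event would appear in the adverse event tables under either reading, so reporting is not at risk; the DLT count is.

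**What to change.** Add one sentence to item 3 of the CABG attribution rules in section 17.3.3, for example:

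> *For WHO Grade 3 or higher or Spilker-severe reactions covered by this item, exclusion from DLT follows WHO-list item 6: the reaction is excluded only if the allergy specialist clearly identifies another cause; if the cause remains undetermined, it counts as a DLT.*

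This is confined to the postoperative reactions that item 3 already covers, and lower-grade reactions stay under the present wording. It applies the standard the plan already states in WHO-list item 6 and needs no new procedure or data. The choice of default is a judgement, since the neighbouring rules differ, but it takes the cautious side, as the plan does for ventricular arrhythmia. The cost is that an occasional reaction unrelated to the gene may count as a DLT, adding three subjects at that dose or, with a second DLT, stopping escalation.

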 - 1-2. If DLT occurs in 1 out of 3 subjects (1/3) → Enroll 3 additional subjects at the same dose
 - 1-2-1. If no DLTs in the additional 3 subjects (1/6) → Proceed to Step 2, enroll 3 more subjects (A)
 - 1-2-2. If 1 additional DLT occurs among the 3 (2/6) → Stop dose escalation
 - 1-3. If DLT occurs in 2 out of 3 subjects (2/3) → Stop dose escalation
2. Step 2: Three subjects are enrolled. DLT is evaluated 4 weeks after the third subject is dosed.
 - 2-1. If no DLTs occur in all 3 subjects (0/3) → Proceed to Step 3, enroll 3 more subjects (B)
 - 2-2. If DLT occurs in 1 out of 3 subjects (1/3) → Enroll 3 additional subjects at the same dose
 - 2-2-1. If no DLTs in the additional 3 subjects (1/6) → Proceed to Step 3, enroll 3 more subjects (B)
 - 2-2-2. If 1 additional DLT occurs among the 3 (2/6) → Stop dose escalation (A)
 - 2-3. If DLT occurs in 2 out of 3 subjects (2/3) → Stop dose escalation (A)
3. Step 3: Three subjects are enrolled. DLT is evaluated 4 weeks after the third subject is dosed.
 - 3-1. If no DLTs occur in all 3 subjects (0/3) → End of clinical trial (C)
 - 3-2. If DLT occurs in 1 out of 3 subjects (1/3) → Enroll 3 additional subjects at the same dose
 - 3-2-1. If no DLTs in the additional 3 subjects (1/6) → End of clinical trial (C)
 - 3-2-2. If 1 additional DLT occurs among the 3 (2/6) → End of clinical trial (B)
 - 3-3. If DLT occurs in 2 out of 3 subjects (2/3) → End of clinical trial (B)

Tolerated dose

Condition	Tolerated dose
A + B + C	C
A + B	B

A	A
---	---

3) Adverse events and laboratory test values

An adverse event is defined as any symptom, sign, or disease that occurs or worsens during the clinical trial, regardless of its relationship to the investigational drug. It is the responsibility of the investigator and study staff to record all adverse events that occur during the clinical trial. Adverse events should be recorded using medical diagnostic terminology; if that is not possible, terms describing observed symptoms and signs reported by the subject should be documented.

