8. Hair	None	Minimal hair loss	Moderate, patchy alopecia	Complete alopecia but reversible	Nonreversible alopecia
9. Infection (specify site)	None	Minor infection	Moderate infection	Major infection	Major infection with hypotension
10. Cardiac					
Rhythm	No change	Sinus tachycardia > 110 at rest	Unifocal PVC, arterial arrhythmia	Multifocal PVC	Ventricular tachycardia
Function	No change	Asymptomatic but abnormal cardiac sign	Transient symptomatic dysfunction; no therapy required	Symptomatic dysfunction responsive to therapy	Symptomatic dysfunction nonresponsive to therapy
Pericarditis	No change	Asymptomatic effusion	Symptomatic; no tap required	Tamponade; tap required	Tamponade; surgery required
11. Neurologic					
State of consciousness	Alter	Transient lethargy	Somnolent < 50% of waking hours	Somnolent > 50% of waking hours	Coma
Peripheral	None	Paresthesias and/or decreased tendon reflexes	Severe paresthesias and/or mild weakness	Intolerable paresthesias and/or marked motor loss	Paralysis
Constipation**	None	Mild	Moderate	Abdominal distention	Distention and vomiting
12. Pain***	None	Mild	Moderate	Severe	Intractable

These guidelines resulted from two international meetings organized on the initiative of the World Health Organization, as published by Miller AB, et al: Cancer 1981; 47: 207

*N, upper limit of normal

** Constipation does not include constipation resulting from narcotics.

*** Only treatment-related pain is considered, not disease-related pain. The use of narcotics may be helpful in grading pain, depending upon the tolerance level of the patient.

[Appendix 6] JNC VII Guide to Prevention and Treatment of Hypertension

Recommendations

Classification and management of blood pressure for adults aged 18 years or older

BP classification	Systolic BP* (mmHg)	Diastolic BP* (mmHg)	Lifestyle modification	Initial drug therapy	
				Without compelling indications	With compelling indications
Normal	Less than 120	Less than 80	Encourage	No antihypertensive drug indicated	Drug(s) for compelling indications. ‡
Prehypertension	120 – 139	80 – 89	Yes		
Stage 1 hypertension	140 – 159	90 – 99	Yes	Thiazide-type diuretics for most. May consider ACEI, ARB, BB, CCB, or combination.	Drug(s) for the compelling indications. ‡ Other antihypertensive drugs (diuretics, ACEI, ARB, BB, CCB) as needed.
Stage 2 hypertension	160 and above	100 and above	Yes	Two-drug combination for most† (usually thiazide-type diuretic and ACEI or ARB or BB or CCB).	

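### Section 17.3.3 discontinues dose escalation for a Grade 3 rhythm event without an event count, which conflicts with the 2/3 and 2/6 escalation rule and leaves the tolerated dose undefined

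*Combined protocol and SAP*

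**What the plan says.** Section 17.3.3, part 1, sets the general rule: "DLT is defined as adverse reactions of Grade 3 or higher according to the WHO Toxicity Scale", or severe on the Spilker scale, within four weeks of administration. It then takes surgical reactions out: "Adverse reactions specific to CABG caused by the surgery itself are excluded from the DLT evaluation".

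Two lists in that section deal with ventricular arrhythmia.

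- The first list (item 5, Arrhythmia) sorts events by cause. It notes that "Ventricular tachycardia and fibrillation may occur due to postoperative bleeding, myocardial dysfunction, or reperfusion injury in chronically ischemic areas", and continues: "If these are clearly related to surgery, such as bleeding from the graft or cardiac tamponade, they are considered surgical complications". Of recurrent arrhythmia that keeps its preoperative pattern it says that "these are not considered caused by gene therapy, but follow-up with Holter monitoring is needed to track any changes".
- The second list goes through the WHO scale and is introduced as surgical reactions left out of the DLT evaluation. Its Rhythm item says that a direct link to the injection is hard to establish and that, "in the interest of patient safety, WHO Grade 3 criteria will be followed and dose escalation will be discontinued".

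In Appendix 5, Grade 3 rhythm is "Multifocal PVC" and Grade 4 is ventricular tachycardia.

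The escalation algorithm (section 17.3.3, part 2) says for Step 1: "If DLT occurs in 1 out of 3 subjects (1/3) → Enroll 3 additional subjects at the same dose". Steps 2 and 3 have the same branch. Section 13.4.6 stops escalation at 2/3 or 2/6 DLTs. Apart from DLT counts, sections 11.4 and 13.4.6 name only cancer and proliferative retinopathy attributed to the gene therapy as reasons to stop.

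**The concern.** The Rhythm item fits neither of the two mechanisms that the protocol defines. As a DLT exclusion, it should have no effect on escalation. As an ordinary DLT, a single event should expand the cohort and not end escalation. As a stand-alone stop, it should appear beside cancer and proliferative retinopathy in sections 11.4 and 13.4.6, and it does not.

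Two other items in the second list have the same gap. The Hemorrhage item discontinues escalation for persistent bleeding at the injection site. The Pericarditis item does so when bleeding at that site is confirmed. Neither gives an event count, and neither is in section 13.4.6.

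The tolerated dose is a primary endpoint and is read from the path taken through Steps 1 to 3. With three subjects per cohort, one event can settle that path. If the text supports more than one path, the choice will be made after the event has been seen.

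**Working it through.** **1. The algorithm as written.** Three dose groups of 3 give 3 × 3 = 9 subjects. If every group is expanded, 3 × (3 + 3) = 18. Both match the plan's target and its maximum, so the 2/3 and 2/6 rule with expansion at 1/3 is the intended general rule.

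**2. One patient, three results.** Take an unexplained multifocal PVC (Grade 3) in 1 of 3 subjects, with no other DLT.

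| Reading of the Rhythm item | Tally | Consequence |
|---|---|---|
| Stand-alone stop | not used | escalation discontinued |
| Ordinary DLT | 1/3 | three more subjects at the same dose |
| Excluded, as the list's introduction says | 0/3 | next dose group opens |

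**3. The tolerated dose that follows.**
- Cohort 1: the 0/3 path awards A. The stopping branches 1-2-2 and 1-3 carry no letter, so a stop here leaves no tolerated dose.
- Cohort 2: the 0/3 path awards B. The 1/3 path awards B or A, depending on the added three. A stop would give A only if it is treated like branches 2-2-2 and 2-3, which the text does not say.
- Cohort 3: the 0/3 path awards C. The 1/3 path awards C or B. There is no higher dose to withhold, and the text does not say whether a discontinuation here means B or C.

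**4. Illustrative size.** The documents give no rate for ventricular rhythm events of Grade 3 or higher. Let *p* be an assumed chance per subject within four weeks, equal across doses and independent between subjects, and let *q* = 1 − *p*. Only these events are considered.

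- One event stops escalation: P(stop in Cohort 1 or 2) = 1 − *q*⁶.
- 3+3 count: P(stop in one cohort) = *s* = 1 − [*q*³ + 3*pq*² × *q*³], and over two cohorts 1 − (1 − *s*)².
- All excluded: 0.

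For *p* = 0.10, the first gives 1 − 0.9⁶ = 0.469. For the second, *s* = 1 − [0.729 + 0.243 × 0.729] = 0.0939, and 1 − 0.9061² = 0.179.

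| Assumed *p* | One event stops | 3+3, one cohort (*s*) | 3+3, Cohorts 1–2 | Excluded |
|---|---|---|---|---|
| 5% | 26% | 2.7% | 5% | 0% |
| 10% | 47% | 9.4% | 18% | 0% |
| 20% | 74% | 29.1% | 50% | 0% |

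All columns except *s* give the chance of not reaching Cohort 3.

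**5. A secondary ambiguity.** For VT or VF with a clear surgical cause, the first list excludes the event from DLT. The Rhythm item states no such exception, although the Pericarditis item below it does set a condition on cause. The Rhythm item can be read as limited to arrhythmia of unclear or reperfusion origin. But the first list also names reperfusion, so the boundary between the two is not drawn.

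**The case against.** The best defence is that the text can be harmonised. A stand-alone stop simply overrides the tally, as cancer and retinopathy do, so there is no contradiction with 0/3. Alternatively, following the WHO Grade 3 criteria may mean only that rhythm events return to the ordinary DLT count. Each reading is coherent, but they lead to different decisions and the sentence does not choose. The first needs an entry in sections 11.4 and 13.4.6 that is missing. The second does not explain why a single event would discontinue escalation. The 0/3 reading is the weakest for a multifocal PVC, because the first list calls that finding abnormal. Without it, two incompatible outcomes still remain.

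A reader might infer several stronger points that the documents do not support.

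- *The lists flatly contradict each other on VT from tamponade after a graft bleed.* If the Rhythm item is confined to unclear or reperfusion causes, that event is excluded under both lists. This is an ambiguity.
- *The preoperative-pattern sentence creates a common conflict.* Exclusion criterion 2 bars uncontrolled ventricular arrhythmia and any history of treatment for it, so few such patients could enter.
- *The event either ends the trial or disappears.* The Rhythm item discontinues dose escalation, not the trial. The event remains an adverse event, counts as MACE if treated, and belongs in the assessment of injection complications (section 17.3.3, parts 3 to 5).
- *Ventricular arrhythmia is the leading cardiac risk of the injection.* Section 13.4.5 lists it after bleeding and ranks neither.

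The probabilities rest on assumed rates, and the 26%, 47% and 74% belong to the strictest reading. The inconsistency itself does not depend on any rate.

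**Conclusion.** The point holds as an internal inconsistency in a decision rule. The Rhythm item has no event count, stands in a list of DLT exclusions, and is absent from the stand-alone stopping criteria, while the algorithm expands at 1/3 and stops only at 2/3 or 2/6. The same Grade 3 event therefore leads to different escalation decisions and tolerated doses depending on the sentence applied. The Hemorrhage and Pericarditis items share the gap. Whether a clear surgical cause exempts a rhythm event is a secondary ambiguity.

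The size is illustrative only. At an assumed 10% per subject, the chance of not reaching Cohort 3 ranges from 0% through 18% to 47% across the three readings. Because the ambiguity bears on a primary endpoint and one event is enough to expose it, it should be resolved before dosing begins.

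**What to change.** Reconcile both lists in section 17.3.3 with sections 11.4 and 13.4.6, Steps 1 to 3 and the matching Synopsis text, so that one rule applies throughout.

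- For each of Rhythm, Hemorrhage and Pericarditis, state whether the discontinuation is a stand-alone stop, to be listed in sections 11.4 and 13.4.6, or a DLT counted in the 3+3 tally.
- State whether the surgical-cause exception in the first list applies to the Rhythm item, including arrhythmia attributed to reperfusion.
- State the tolerated dose that follows from a discontinuation in each cohort, including Cohort 1, where the stopping branches carry no letter, and Cohort 3, where no higher dose exists.

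The choice of clinical rule belongs to the sponsor and the investigator and should be fixed before the first subject is dosed. The cost is protocol wording: edits in section 17.3.3, matching lines in sections 11.4 and 13.4.6 if any stand-alone stop is kept, and the Synopsis. No new data or assessments are needed.

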- The adverse event is equally likely to be caused by the investigational product as by other possible causes.
- The adverse event resolves upon discontinuation of the investigational product (if done).

4) Probably not related

- There is evidence that the investigational product was administered.
- There is a more likely alternative cause for the adverse event.
- The adverse event does not resolve or shows an unclear outcome upon discontinuation (if done).
- The rechallenge result is negative or unclear (if done).

5) Definitely not related

- The subject did not receive the investigational product, or
- The temporal relationship between administration and the adverse event is not appropriate, or
- There is a clear alternative explanation for the adverse event.

If a dose-limiting toxicity (DLT) or an unexpected Grade 3 or higher adverse event occurs, the causality between the adverse event and the investigational product must be assessed by two or more investigators.

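### The cardiac-function line in 17.3.3 removes a whole toxicity item from the DLT count without asking the cause, so read literally the tolerated-dose rule cannot count drug-caused cardiac dysfunction

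*Combined protocol and SAP*

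**What the plan says.** Section 17.3.3 defines a DLT as a reaction of WHO Grade 3 or higher, or Spilker severe, within 4 weeks of administration, leaving out reactions associated with CABG. The exclusion list set against the WHO items carries the same limit: "the following reactions caused by surgery are excluded from the DLT (Dose-Limiting Toxicity) evaluation".

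Under the cardiac heading of that list, the function item reads: "Most patients have impaired cardiac function due to the nature of cardiac surgery; thus, excluded from DLT evaluation". Appendix 5 shows what is removed. Grade 3 is "Symptomatic dysfunction responsive to therapy" and Grade 4 is "Symptomatic dysfunction nonresponsive to therapy".

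For mediastinitis, 17.3.3 relates the event to the injection "only if the sterile distilled water used to dissolve the gene tests positive in culture for the same pathogen isolated from the patient". For every other case it states: "Otherwise, it is determined to be an infection related to CABG".

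Section 18.1 requires that, for a DLT or an unexpected Grade 3+ event, "the causality between the adverse event and the investigational product must be assessed by two or more investigators".

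**The concern.** The general rule excludes an event because of what caused it in that patient. The cardiac-function line excludes an event because most patients have something like it. A statement about the population thus replaces a judgment about the case.

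The product is injected into the myocardium, so depressed function is a plausible local toxicity. DLT and tolerated dose are primary safety items, and the tolerated dose follows mechanically from the DLT count. If the line is applied as written, the rule that selects the dose has no sensitivity to this toxicity, however often it occurs.

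The mediastinitis rule raises a lesser problem. Attribution to the injection depends on one laboratory result, and the plan does not say how that result would be obtained.

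**Working it through.** **1. The cardiac-function line beside its neighbours (17.3.3).**

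- Hemorrhage: treated as surgical, but persistent bleeding where the gene was injected stops escalation.
- AST/ALT: excluded up to stated levels if due to transfusion or ischemia.
- Proteinuria and hematuria: excluded if another named cause explains them.
- Allergy: excluded when the cause is clearly identified.
- Rhythm: attribution is called difficult, yet Grade 3 is kept and stops escalation.
- Pericarditis: stops escalation only with confirmed injection-site bleeding.
- Cardiac function: no cause, site or grade condition.

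Pulmonary findings that follow from reduced cardiac function are also excluded, so breathlessness from pump failure does not provide another route into the count.

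**2. Does another rule catch it?**

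- The criteria in 13.4.6 for discontinuing escalation are DLT counts, cancer and proliferative retinopathy.
- MACE (17.3.3, item 4) covers cardiac death, infarction, treated ventricular arrhythmia and hospitalization for target vessel revascularization. It does not name dysfunction or heart failure.
- The general adverse-event tables would show it, and perhaps the open category of other injection complications. Neither feeds the tolerated-dose table.
- Section 13.4.6 also makes each doubling conditional on no safety issue arising, but gives no operational criterion.

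**3. Could a case be judged individually?** Some data exist. Section 11.2 bars symptomatic heart failure and LVEF below 25%, so baseline is screened. Echocardiography is done at screening and on Day 7, and NYHA class is recorded at Weeks 2 and 4 (14.1 to 14.3), all within the DLT window or before it.

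**4. The plan's own figures.** Three doses × 3 subjects = 9, and three doses × 6 = 18. Both stated enrolment figures reproduce.

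**5. What exclusion does to the 3+3 rule.** A dose passes with 0/3, or with 1/3 followed by 0/3. With DLT probability p per subject:

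P(pass) = (1−p)³ + 3p(1−p)² × (1−p)³ = (1−p)³ + 3p(1−p)⁵

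The documents give no rate of drug-caused dysfunction, so p is assumed. With no other DLT:

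| Assumed p | P(pass), events counted | P(pass), events excluded |
|---|---|---|
| 10% | 0.906 | 1.000 |
| 20% | 0.709 | 1.000 |
| 33% | 0.296 + 0.132 = 0.428 | 1.000 |
| 50% | 0.125 + 0.047 = 0.172 | 1.000 |

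Allowing an assumed 5% of other DLTs and 30% dysfunction, taken as independent, p = 1 − 0.95 × 0.70 = 0.335. The dose then passes with probability 0.425 if dysfunction counts and 0.973 if it does not.

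**6. Mediastinitis.** Section 17.3.3 gives a background of 2–3%. The chance of at least one case is 1 − (1−p)ⁿ:

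- n = 9: 1 − 0.98⁹ = 16.6% to 1 − 0.97⁹ = 24.0%
- n = 18: 30.5% to 42.2%

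So the rule could well be used. Yet no diluent retention or culture appears in the preparation steps (13.4.1), the test lists (14.1 to 14.3) or the synopsis schedule.

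**The case against.** **The heading may already limit the line.** The list is introduced as covering reactions caused by surgery, so the function item could be read as surgical dysfunction only. This reading is possible. It sits badly with the item's own logic, which goes from most patients straight to exclusion, and two defensible readings of an escalation rule are themselves a reason to reconcile the text.

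**A reader might infer that the primary endpoint cannot register any drug-caused event in the injected organ.** The documents do not support that. Grade 3 rhythm toxicity, persistent injection-site bleeding, and pericarditis with confirmed injection-site bleeding all still affect escalation. DLT and tolerated dose are two of five primary safety items; adverse reactions, MACE and injection complications are the others.

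**A reader might infer that mediastinitis will always go to surgery.** That is not shown either. The rule tests the diluent, so using the full 4 mL of reconstituted product in Cohort 3 does not prove that nothing is left to culture, and a for-cause culture need not stand in a visit schedule. What stands is that no retention or culture procedure is stated.

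**Nor do the two rules demonstrably switch off 18.1.** An unexpected Grade 3+ dysfunction or infection would still call for two investigators. Expectedness depends on the Investigator's Brochure, which is not available here. Dysfunction barred from DLT and regarded as expected after surgery might not trigger the review.

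**The exclusion has a sound purpose.** There is no control group, Grade 3 includes dysfunction that responds to therapy, and inotropes are listed as common after surgery (13.5.1). At an assumed 30% surgical background with every case counted, one dose passes with probability 0.494 and all three with 0.494³ = 0.121. This stands: the defect is the missing case-level attribution, not the existence of an exclusion.

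**The 1.00 is true by construction.** It follows from setting the count to zero and assuming no other DLT. It illustrates the mechanism and estimates nothing about this product.

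**Conclusion.** The point holds for the DLT and tolerated-dose component. Read literally, the cardiac-function line keeps drug-caused Grade 3 or 4 dysfunction out of the DLT count, contrary to the caused-by-surgery condition above it, and no other stated escalation criterion names that toxicity. The mediastinitis rule is a secondary weakness: its only route to attribution may not be available in practice.

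The size depends on a rate the documents do not give. At assumed rates of 33% and 50%, with no other DLT, the chance of passing one dose level moves from 0.43 and 0.17 to 1.00. Allowing for other DLTs narrows the gap without closing it (0.425 against 0.973 in the case worked above). The conclusion assumes the literal reading and does not extend to the primary endpoint as a whole.

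**What to change.** 1. The sponsor should reconcile the cardiac-function line and the mediastinitis rule in 17.3.3 with the caused-by-surgery condition in the same section and with the causality assessment in 18.1. No particular stopping rule is proposed here.

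2. Tabulate all WHO Grade 3+ events in the 4-week window by dose group before any exclusion, with the reason and causality assessment for each excluded event. Present the table beside the tolerated-dose conclusion and state whether any exclusion changed a cohort's count against the 3+3 thresholds.

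Do not report a second tolerated dose. The rule is path-dependent: if one of three subjects has a DLT only on the unexcluded count, the three expansion subjects were never enrolled and that dose is undefined. At an assumed 33%, exactly one in three occurs in 3 × 1/3 × (2/3)² = 44% of cohorts.

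Cost: protocol wording and one table. Severity by dose group is already planned, so only the 4-week restriction and the exclusion reasons are new. The tolerated-dose statement may look less favourable.
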